## 5.0 STUDY CALENDAR

The pre-study intervals are guidelines only. Laboratory and clinical parameters during treatment are to be followed using best clinical judgment of the responsible attending physician. It is expected that patients on this study will be cared for by physicians experienced in the treatment and supportive care of patients with PAC treated with SBRT. Registration is defined as the date the patient consents.

### Pre-Randomization Testing

- To be completed ≤ 30 Days before randomization: All laboratory studies, history and physical.
- Minor changes to the assessment schedule may be made to accommodate holidays, administrative closures, etc, which if necessary, are not considered as significant deviations by the Sponsor. If possible, site should contact the Sponsor prospectively to address rescheduling protocol assessments and data handling.
- Standard of care evaluations may be utilized for screening, provided the assessments are clearly documented as standard of care in the source and meet protocol requirements and timelines.

| Tests & Observations   | Screening/ Prior to Randomization* | Baseline         | Last Day of SBRT | 4B weeks post SBRT (optional) | 7B weeks post SBRT | 12 weeks post SBRTB | Post Tx Follow-up** |
|---|---|-------------------------|-------------------------|---|--------------------------------------|---------------------------------------|----------------------------|
|   | Within 30 days of randomization           | Day -21 to 1 (pre-dose) | Day 5                   | Day 33  | Day 54                               | Day 89                                |                            |
|   |   |                         | +/-2 days               | +/-7 days                                       | +/-7 days                            | +/-5 days                             | +/-28 days                 |
| Medical and Disease History (including disease status and pathology review)   | X (1)                                     | X (1)                   |                         |   |                                      |                                       |                            |
| Physical, weight, ECOG PS (May be physician clinic visit at baseline visit)   | X (1)                                     | X (1)                   | X (1)                   |   | X (1)                                | X (1)                                 | X (1)                      |
| Pulse, BP   | X   | X (1)                   | X (1)                   |   | X (1)                                | X (1)                                 | X (1)                      |
| Height \$   | X   |                         |                         |   |                                      |                                       |                            |
| Adverse Event Assessment†   |   | X (1)                   | X (1)                   | X (1)   | X (1)                                | X (1)                                 | X (1)                      |
| PRO-CTCAE   | X (2)                                     | X(2)                    | X                       | X   | X                                    | X                                     | X                          |
| Fatigue/QOL/Physical/Mental LASA Assessment   | X (2)                                     | X(2)                    | X                       | X   | X                                    | X                                     | X                          |
| Endoscopy with Fiducial placement for CT guided on-line positioning (not necessary for MR-linac treatments), core biopsies, cytologic brushings | X*  |                         |                         |   |                                      |                                       |                            |
| Endoscopy with duodenal evaluation, core biopsies if possible, cytologic brushings  |   |                         |                         |   |                                      | X (5)                                 |                            |

|  |       |       |       |       |       |       |       |
|--|-------|-------|-------|-------|-------|-------|-------|
| Radiation Simulation (>5 business days prior to SBRT and following eligibility)***         | X     |       |       |       |       |       |       |
| Laboratory Studies  |       |       |       |       |       |       |       |
| Electrocardiogram (ECG)  | X     |       |       |       |       |       |       |
| CBC, Differential, Platelets   | X     | X     | X     | X     | X     | X     | X     |
| Chemistry (Serum Creatinine, Electrolytes, AST, ALT, Alk. Phos., Albumin, Total Bilirubin) | X     | X     | X     | X     | X     | X     | X     |
| Pregnancy Test (#)   | X     |       |       |       |       |       |       |
| Tumor marker (CA 19-9)   | A     | A     | A     | A     | A     | A     | X     |
| Blood and Tissue Collection for Correlatives   |       | X (4) | X (4) | X (4) | X (4) | X (4) | X (4) |
| Evaluation for Resectability (7)   | X     |       |       |       | X     |       |       |
| Staging   |       |       |       |       |       |       |       |
| Pancreatic Protocol CT(3,6) (for resectability assessment)                                 |       |       |       |       | X     |       |       |
| MRI abdomen w/ and w/o contrast (for assessment of small bowel toxicity), is possible.     | X (3) |       |       |       |       | X (3) |       |
| Restaging CT Scan of Chest/Abd/Pelvis  | X (3) |       |       |       |       | X (3) | X(3)  |
| Randomization****  |       | X     |       |       |       |       |       |

\* Endoscopy for fiducial placement and biopsies may occur anytime between screening and radiation simulation

\*\* After the 12 week visit, patients will continue in follow-up with physical examinations, labs, and staging scans every 3 months (+/- 28 days) post-SBRT until they have reached 36 months post-SBRT or until local progression. Thereafter, clinical status information is required every 6 months for 5 years post-SBRT, to include survival information and toxicity data. This information may be obtained via telephone call if patient is lost to clinic follow up. For patients who discontinue treatment for progressive disease or are removed from protocol treatment, survival information is required every 6 months for 5 years post-SBRT. Adverse events including radiation toxicity up to 1 year post-SBRT will be assessed during visits and phone calls, and recorded in the case report form (See section 9.3 for details).

\*\*\* Simulation should be within 30 days of SBRT. If simulation is done > 2 weeks prior to treatment start, a verification simulation should be performed in the week prior to treatment start.

\*\*\*\* Randomization will occur following completion of the radiation simulation. See Study Manual for details on the registration and randomization process.

1 Medical and Disease History, including pathology, collected within the Screening and Baseline Period will include information deemed medically-relevant by the Investigator (or designee). May be performed by physician, NP, or PA responsible for oncologic care of the patient. Vitals may be collected by RN or MA.

2 To be completed ONCE prior to treatment. The study files will contain examples and IRB approval of the assessments.

3 Chest scans must be CT or chest X-ray. Abdominal baseline and restaging scans can include either a pancreatic protocol CT or MRI, although pancreatic protocol CT is preferred. The CT must be acquired with at least a 5 mm or less slice thickness. Initial scans for determining eligibility and resectability status will be reviewed at the treating institution and central review will not be required except in cases of uncertainty. In case of contraindications (eg pacemaker, severe claustrophobia, etc) a high quality CT scan can be acquired.

4 Correlative blood collection will occur at Baseline, at day 2 (pre- treatment), day 5 (pre- treatment), week 7 and week 12. The blood draw at week 4 and all Follow Up time points will be optional. Tissue collection is required at Baseline and week 12. Please see Table 7 for sample collection timepoints.

5 Endoscopic evaluation approximately 12 weeks post radiation.

6 The resectability imaging will be done based on clinical necessity per the surgical oncologist.

7 Resectability will be assessed at respective institutions.

† AEs are to be collected starting at baseline and through 1 year post SBRT. Routine AEs are to be collected starting after randomization. See section 9.0 AE definition. See section 9.3 for expedited reporting of SAEs.

# For women of age 18-55 without hysterectomy or tubal ligation. Must be done ≤ 14 days prior to study entry (dosing). Testing should be done per institutional standard.

\$ A previous height may be utilized if within 6 months of consent

A Previously obtained CA19-9 may be used if within < 28 days prior to randomization. Subsequently, CA 19-9 may be performed +/- 14 days from the scheduled date. During treatment, CA 19-9 should be performed every 28 days. For patients who have normal CA 19-9 levels at baseline, continued testing of CA 19-9 is not required.

B Research coordinator or RN will call patient weekly up to the week 7 visit, and again at week 10 to confirm no adverse events between clinical visits. The week 4 visit is optional. If the patient is not seen in the clinic, the patient should be contacted by phone this week.

## 6.0 RADIATION DELIVERY

### 6.1 Radiotherapy Technical Factors

#### 6.1.1 Eligibility criteria for SBRT

In order to ensure safety, patients must meet the following criteria in order to proceed with SBRT:

- Patients must have no evidence of active duodenal or gastric ulcers or direct tumor invasion of the bowel or stomach on pre-SBRT endoscopy. Previous history of ulcers >30 days prior to treatment with no active bleeding or symptoms are eligible for treatment.
- Patients should not be treated with SBRT if SBRT-specific organ at risk (OAR) constraints (listed in [section 6.3](#)) cannot be met.
- Patients must be able to undergo 4D CT simulation to assess tumor motion with respiration and able to comply with breath hold for motion management.
- Patient must not have any contraindication to contrast administration at simulation, including contrast allergy refractory to premedication at the discretion of the treating physician.
- Patient must have a functioning metal stent in place if biliary or duodenal stent is required.

#### 6.1.2 Technical Factors including Treatment Delivery and Fiducial Placement

- Only  $\geq 6$  MV photons are permitted for SBRT.
- Particle therapy is not permitted.
- Static IMRT or VMAT must be used; 3DCRT is not permissible. It is recommended that 6-12 coplanar static IMRT fields or 1-3 arc fields (VMAT/Rapid-Arc) be used in the radiation treatment plan. Flattening Filter Free (FFF) treatment is allowed.
- Both treatments with CT and MRI guidance for positioning are accepted, for CT guided positioning 1-5 (preferably  $\geq 3$ ) fiducial markers should be placed for targeting purposes. These markers will be placed directly at the tumor periphery and/or within 1 cm of the tumor (normal pancreas) under endoscopic ultrasound at any time prior to radiation simulation. Fiducials are optional for MR Linac based treatment. Simulation can follow fiducial marker placement on the same day in case of an uncomplicated positioning endoscopic procedure, however, some hours of delay are recommended to reduce the risk of post-positioning swelling. The simulation quality and timing is at the discretion of the treating physician.
- Simulation should be done  $\leq 30$  days prior to first fraction of SBRT.
- If simulation is done > 2 weeks prior to treatment start, a verification simulation should be performed in the week prior to treatment start.
- Patients will be positioned supine, arms above the head, in a custom immobilization device.
- Administration of IV and oral contrast is required for target and normal tissue delineation unless patient has a contrast allergy refractory to premedication or at the discretion of the treating physician. A pretreatment renal scan to assess kidney differential will be performed prior to initiation of treatment if clinically appropriate per the treating physician.

- A 4D CT scan may be performed to assess respiratory motion. If > 5 mm of tumor motion in any direction is noted, then the use of breath-hold (BH) technique is required. If BH is utilized, 3-5 BH scans will be performed for reproducibility. If there is < 5 mm tumor motion on 4DCT and patient cannot tolerate BH, treatment planning may be done in free breathing using 4D CT.
- MRI or PET simulation may be optionally performed in the treatment position and later fused to the CT simulation scan to assist in target volume delineation, but this is not required.
- Patients will be treated on CT- or MRI guided linacs, for all daily imaging is required for position verification (CBCT, daily KV with fiducial tracking or MRI positioning).
- Deformable adaptive repositioning and planning is accepted done on-line or off-line, while well documented as e.g. adapted plan1...6
- If not clinically contraindicated, patient will be placed on proton pump inhibitor for duration of treatment and 90 days post treatment.

## 6.2 Target Delineation

[figure not shown]
### 6.2.1 Required Structures

- GTV: Primary pancreatic tumor as delineated on all available pre-treatment imaging and CT simulation
- iGTV: GTV expanded to encompass tumor in all phases of 4DCT or all BH scans obtained during simulation.
- iGTV\_Exp = iGTV + 3mm (uniform expansion)
- TVI: The segment of portal vein, SMV, SMA, and/or celiac artery that is in direct contact with tumor. TVI structures will be contoured to include entire radial extent of any vessel that contacts tumor. For example, the SMA TVI will include the entire 360-degree extent of SMA even if there is only 90-degree involvement of the SMA by tumor. This radial contour should extend superiorly and inferiorly on each axial slice where there is GTV contoured.
- TVI\_Exp: TVI + 3mm (uniform expansion)
- Fiducials: Fiducials and/or clips should be contoured separately starting superiorly and moving inferiorly in numeric order.
- Fiducials\_Exp: Fiducials + 3mm (uniform expansion)
- iDuodenum: Duodenum contoured to encompass tumor in all treatment phases of 4DCT or all BH scans obtained during simulation.
- PRV\_Duo: iDuodenum + 5mm (uniform expansion)
- iStomach: Stomach contoured to encompass tumor in all treatment phases of 4DCT or all BH scans obtained during simulation.
- PRV\_Stom: iStomach + 5mm (uniform expansion)
- iBowel: Any other small bowel in the treatment area, contoured to encompass tumor in all treatment phases of 4DCT or all BH scans obtained during simulation.
- PRV\_Bowel: iBowel + 5mm (uniform expansion)

- $PRV\_GI = PRV\_Duo + PRV\_Stom + PRV+Bowel$
- Bilateral kidneys, liver, spinal cord and spleen contoured per institutional guidelines. No PRV structures are required.
- Prescription Dose will be prescribed to different PTV volumes according to the dose level (figure 10):
- $PTV\_1 = iGTV\_Exp + TVI\_Exp$ . Prescription dose to this structure is 6.6Gy in 5 fractions at all dose levels to the 95% isodose line.
- $PTV\_2 = PTV1 - PRV\_GI$ . Prescription dose to this structure will be according to PTV2 dose for assigned dose level to the 95% isodose line.

Safety Note: SBRT feasibility is judged by the treating physician.

- Tumor volume is not a restrictive criteria, however, the PTV2 needs to be sufficiently covered at least 60% of the prescribed dose, while still meeting the normal tissue constraints
- Radiological or endoscopic signs of tumor infiltration in bowel structures need to be well described before SBRT. Aside from bulging tumor masses in the bowel lumen, tumor infiltration in itself it is not an exclusion criteria but informs judgement of the physician to perform SBRT. All suspect areas need to be included in the PTV1 and sufficiently covered for at least 60% of the (6.6Gy) prescribed dose while still meeting the normal tissue constraints

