#### **4.2 Exclusion Criteria:**

1. Prior radiation therapy to the abdomen that would overlap with treatment field
2. Prior surgical resection of pancreatic tumor
3. Receiving any approved or investigational anti-cancer agent other than those provided for in this study
4. Uncontrolled or active gastric or duodenal ulcer disease within 30 days of dosing
5. Visible invasion of tumor into the lumen of the bowel or stomach on endoscopy (Note: Radiological infiltration into bowel is allowed, unless deemed clinically unsafe.)
6. Residual or ongoing  $\geq$  Grade 3 non-hematologic toxicity from chemotherapy
7. Contraindication to IV contrast
8. Concurrent participation in another interventional clinical trial or use of another investigational agent within 30 days of study consent Note: Patients who are participating in non-interventional clinical trials (e.g., QOL, imaging, observational, follow-up studies, etc.) are eligible, regardless of the timing of participation.
9. Uncontrolled intercurrent illness including, but not limited to, ongoing or active infection, symptomatic congestive heart failure, unstable angina pectoris, renal failure, cardiac arrhythmia, or psychiatric illness that would limit compliance with treatment
10. Second primary malignancy within the last 5 years, unless treated definitively and with low risk of recurrence in the judgment of the treating investigator
11. Known history of HIV or active hepatitis B/C (patients who have been vaccinated for hepatitis B and do not have a history of infection are eligible)

12. Female patients who are pregnant or breastfeeding
13. Women of child-bearing potential who are unwilling or unable to use an acceptable method of birth control to avoid pregnancy for the entire study period and for 30 days after the last dose of GC4419. Acceptable methods include, but are not limited to, barrier methods, IUD, and birth control pills. This includes any woman who has experienced menarche but has not undergone successful surgical sterilization or is not postmenopausal (defined as amenorrhea for at least 12 consecutive months, or women on hormone replacement therapy with serum FSH levels greater than 35 mIU/mL). A negative urine or serum pregnancy test must be obtained within 14 days prior to the start of study therapy in all women of child-bearing potential.

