### 6.3 Treatment Planning Guidelines and Dose Constraints

Prescription dose to PTV\_1 must cover 95% of the target volume. There are no formal coverage constraints on PTV\_2, but they should be maximized while maintaining OAR constraints at the treating physician's discretion. Recommended and mandatory dose constraints are outlined in Table 2.

Table 2. Dose Constraints Recommended for Treatment Planning

| Description      | Planning System Name | Constraints            |
|------------------|----------------------|------------------------|
| PTV_1            | PTV_1                | V33 > 95%*   |
|                  |                      |                        |
| OAR       |                      | Constraints     |
| Duodenum         | iDuodenum            |                        |
|                  |                      | V30 < 3cc*   |
|                  |                      | V35 < 1cc*   |
|                  |                      | V40 < 0.5cc* |
| Small Bowel      | iBowel               |                        |
|                  |                      | V30 < 1cc*   |
|                  |                      | V35 < 0.1cc* |
|                  |                      | V40 < 0.5cc* |
| Stomach          | iStomach             |                        |
|                  |                      | V30 < 2cc*   |
|                  |                      | V35 < 1cc*   |
|                  |                      | V40 < 0.5cc* |
| Liver            | Liver                | V12 < 50%*   |
| Combined Kidneys | Kidneys              | V12 < 75%*   |
| Spinal Cord      | Spinal_Cord          | V20 < 1cc*   |
| Spleen           | Spleen               | Mean < 2 Gy (optional) |

\* Notation indicates required mandatory constraints to be met in order to proceed with SBRT; Other constraints are recommended as reasonably achievable.

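### Section 6.1.1 bars patients with direct bowel invasion on endoscopy whom the Safety Note in Section 6.2.1 allows, and nothing says which rule prevails

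*Combined protocol and SAP*

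**What the plan says.** Three places in the combined protocol and SAP address tumour growth into the gut.

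- **Section 4.2, exclusion 5 (also in the Synopsis)** excludes "Visible invasion of tumor into the lumen of the bowel or stomach on endoscopy". Its note adds: "Radiological infiltration into bowel is allowed, unless deemed clinically unsafe".
- **Section 6.1.1**, a list of conditions for proceeding with SBRT that is introduced as a safety measure, states: "Patients must have no evidence of active duodenal or gastric ulcers or direct tumor invasion of the bowel or stomach on pre-SBRT endoscopy". It has no lumen qualifier.
- **Section 6.2.1, Safety Note**, begins "Radiological or endoscopic signs of tumor infiltration in bowel structures need to be well described before SBRT" and continues "Aside from bulging tumor masses in the bowel lumen, tumor infiltration in itself it is not an exclusion criteria". Infiltration short of that informs the physician's judgement on whether to give SBRT.

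The same Safety Note requires suspect areas to lie inside PTV1 and to be "sufficiently covered for at least 60% of the (6.6Gy) prescribed dose" while the normal-tissue constraints are met. Section 6.3 says the PTV_1 prescription "must cover 95% of the target volume", and Table 2 makes V33 >95% mandatory. Section 6.6.1 classes a PTV_1 minimum dose under 93% of prescription as an unacceptable deviation.

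**The concern.** Sections 6.1.1 and 6.2.1 both govern whether a patient may go on to SBRT, and for one kind of patient they give opposite answers. A site cannot follow both, and Section 4.6.1 leaves the initial eligibility decision to the treating institution, with up to 7 sites planned.

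This is first a safety matter, because Section 6.1.1 presents its list as a safety gate. It also touches the primary endpoint. Section 12.1 defines toxicity for dose finding as related grade 3-4 GI toxicity or death within 90 days, and Section 1.2.4 ties SBRT toxicity to how close the tumour lies to duodenum, stomach and small bowel. Bowel infiltration is therefore plausibly prognostic for the endpoint. Dose levels within an arm are filled sequentially in cohorts of 3 (Section 12.5), so nothing balances such patients across levels. Few events are needed to matter: Section 12.8 describes a minimum of 2 of 5 patients with dose-limiting toxicity as what would mark a level as too high.

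**Working it through.** **Step 1: set the three rules side by side.**

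| Finding before SBRT | Exclusion 5 | Section 6.1.1 | Section 6.2.1 Safety Note |
|---|---|---|---|
| Bowel, radiological only | Allowed unless judged unsafe | Not addressed | Allowed, physician's judgement |
| Bowel, on endoscopy, not visibly into the lumen | Not barred | Barred | Allowed, physician's judgement |
| Bowel, on endoscopy, into the lumen but no bulging mass | Barred | Barred | Allowed, physician's judgement |
| Bowel, bulging mass in the lumen | Barred | Barred | Barred |
| Stomach, on endoscopy, not visibly into the lumen | Not barred | Barred | Silent |
| Stomach, on endoscopy, into the lumen | Barred | Barred | Silent |

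The second and third rows are the contradiction. Both describe endoscopic bowel invasion short of a bulging luminal mass; 6.1.1 bars it and 6.2.1 allows it. No section states an order of precedence. Inclusion 3 gives the investigator discretion over limited bowel involvement, but it does not say that this discretion overrides the mandatory wording of 6.1.1.

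**Step 2: the coverage sentence.** Table 1 gives PTV1 as 33 Gy in total (6.6 Gy × 5) at every dose level.

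- Floor for suspect areas in 6.2.1: 0.60 × 33 = 19.8 Gy.
- Unacceptable-deviation limit in 6.6.1: 0.93 × 33 = 30.69 Gy.

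A suspect area receiving at least 19.8 Gy but less than 30.69 Gy satisfies 6.2.1 and fails 6.6.1. The size of the area is irrelevant, because 6.6.1 looks at the minimum dose anywhere in PTV_1 and 6.2.1 puts the area inside PTV1.

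V33 >95% is a different measure. It is a volume criterion and lets just under 5% of PTV_1 receive less than 33 Gy. If the under-dosed part of PTV_1 is smaller than that, one plan can meet both V33 >95% and the 60% floor. If it is larger, the plan fails V33.

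**Step 3: can the effect on dose finding be sized?** The toxicity limit is 0.15 (Section 12.6) and the prior mean toxicities at levels 2 and 3 are 0.07 and 0.10 (Table 5). Take the prior mean p0 as the rate without infiltration and assume a rate p1 with it. The share of infiltrated patients that lifts the average to 0.15 is f = (0.15 − p0)/(p1 − p0).

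| Assumed p1 | Level 2, p0 = 0.07 | Level 3, p0 = 0.10 |
|---|---|---|
| 0.20 | 0.08/0.13 = 62% | 0.05/0.10 = 50% |
| 0.30 | 0.08/0.23 = 35% | 0.05/0.20 = 25% |
| 0.40 | 0.08/0.33 = 24% | 0.05/0.30 = 17% |

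The p1 values are assumptions. The documents give neither a toxicity rate for infiltrated patients nor their expected share, and the answer runs from 17% to 62%. The direction is clear; the size is not.

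**The case against.** The best reply is that these are successive gates. Exclusion 5 governs entry, 6.1.1 governs proceeding to SBRT, and a careful site applies the stricter. Section 11.2 even provides for patients found ineligible for SBRT after randomisation. This works for exclusion 5 against 6.1.1. A reader might infer a three-way conflict for bowel and stomach alike, but the documents do not support that: 6.2.1 names bowel only, so for the stomach all that remains is the lumen qualifier, and cumulative gates can explain it.

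The reply does not rescue 6.1.1 against 6.2.1. Both concern the same decision, 6.2.1 expressly includes endoscopic signs, and it leaves such patients to judgement and sets planning requirements for the suspect areas. One could treat infiltration and direct invasion as different degrees, or visible luminal invasion and a bulging mass as the same thing, but the text defines neither equivalence.

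On coverage, a reader might infer that the 60% sentence flatly contradicts the mandatory V33 >95%. It does not, as step 2 shows; the conflict is with 6.6.1. It can also be said that 6.6.1 is not meant literally, since its upper limit (1.10 × 33 = 36.3 Gy) lies below the 50 Gy or more prescribed to PTV_2, which is part of PTV_1. That is a reason to clarify 6.6.1 at the same time. It does not reconcile the two minimum doses.

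There are real mitigations. Radiological infiltration is allowed anyway, so only the endoscopic group is in dispute. Escalation is confined to PTV_2, which excludes the GI planning risk volume, and the bowel and stomach constraints are mandatory. These lower the likely effect but do not say who may be treated. Central review of the first three plans per site examines treatment plans and is not described as a check of endoscopic eligibility.

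**Conclusion.** The contradiction between Sections 6.1.1 and 6.2.1 on endoscopic bowel invasion stands on the wording alone, and exclusion 5 adds a third wording. The conflict between the 60% floor and the 93% minimum dose also stands, provided the 60% sentence is read as a dose floor; its tension with V33 >95% is weaker.

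The consequence for dose finding is a possibility. Differing readings may change which GI-risk patients are treated at each level. They may also change who is counted, because Section 11.2 leaves patients found ineligible for SBRT after randomisation out of the 48 and out of the final analyses. The study calendar places endoscopy before simulation and randomisation after it, so this second route should be uncommon.

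Two stronger inferences are not supported. One is that sites will in fact enrol different risk mixes: nothing in the documents shows that they read the rule differently. The other is that case mix would appear as a drug effect: GC4419 or placebo is assigned at random, so only chance imbalance between arms is expected. No numerical size is claimed.

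**What to change.** The investigators and sponsor should replace exclusion 5, the Section 6.1.1 condition and the Section 6.2.1 sentence with one rule, stated once and cross-referenced. It should say which endoscopic and which radiological findings bar SBRT, for bowel and for stomach. They should also reconcile the 60% sentence with Sections 6.3 and 6.6.1 and say which governs suspect bowel areas inside PTV_1. Which rule is right is a clinical decision on which this review takes no view.

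Record infiltration status (none, radiological only, endoscopic) at baseline before randomisation, and list it descriptively beside each patient's 90-day toxicity. A formal breakdown is not worthwhile: three classes by three dose levels is nine cells in an arm of 24, or 24/9 ≈ 2.7 patients per cell.

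The cost is amendment wording and one case report form field, with no new procedure. Eligibility may narrow slightly if the stricter wording is kept.
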